## 6.13 Clinical Laboratory Tests (Safety)

Safety laboratory tests will be performed at the time points specified in Table 1 and sent to a Central Laboratory. Blood samples sent to the local laboratory for the purposes of determining study eligibility must be repeated and sent to the central laboratory following enrollment. Blood and/or urine will be collected at LFU only if the subject had an abnormal (high/low flag) result at TOC. Additional tests may be performed at the discretion of the Investigator if deemed clinically appropriate. Subjects treated as outpatients must agree to return to the site for blood draws as indicated in Table 1 (i.e.,  $96 \pm 24$  hour post first dose [see Section 6.1.1], EOT, and TOC visits).

A full list of the clinical laboratory tests that will be performed and analyzed can be found in Appendix 1. A urine pregnancy test will be performed at the site on all females unless surgically sterile or at least 2 years post-menopausal. A negative urine pregnancy test is required prior to randomization. Serum must be collected on Day 1 prior to 1st dose and sent to the central lab for confirmatory testing.

Any safety laboratory results outside the normal range will be repeated at the discretion of the Investigator and will be evaluated by the Investigator or designee as "clinically significant" or "not clinically significant." Any clinically significant value should be repeated as necessary and followed until resolution.

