- A by-pathogen microbiological response of persistence and a by-subject microbiological response of failure at the EOT Visit will be carried forward to the TOC Visit. If a followup specimen for culture was not obtained and the pathogen/subject was not a microbiologic persistence/failure at EOT, microbiological response at the TOC Visit will be determined based on IACR at the TOC Visit. If the IACR at the TOC Visit is indeterminate, the microbiological response at the TOC Visit will be indeterminate, unless a followup specimen for culture was obtained.
- A by-pathogen microbiological response of persistence and a by-subject microbiological response of failure at the TOC Visit will be carried forward to the LFU Visit. If a followup specimen for culture was not obtained and the pathogen/subject was not a microbiologic persistence/failure at TOC, microbiological response at the LFU Visit will be determined based on IACR at the LFU Visit. If the IACR at the LFU Visit is indeterminate, the microbiological response at the LFU Visit will be indeterminate, unless a followup specimen for culture was obtained.
- For the analysis of microbiological response at the EOT, TOC and LFU Visits in the microITT and microITT-2 Analysis Sets, where microbiological response may be missing (indeterminate), all subjects who meet the analysis set criteria will be included in the denominator.
- For the analysis of microbiological response at the EOT, TOC and LFU Visits in the ME Analysis Sets, subjects with a missing (indeterminate) microbiological response will not be included in the analysis, since by definition, subjects in the ME Analysis Sets cannot have a missing microbiological response.

For all other outcome measures, missing data are handled as follows:

- Missing values for individual data points will remain as missing. Missing values will not be imputed and only observed values will be used in data analyses and presentations.
- When individual data points are missing, categorical data will be summarized based on reduced denominators (ie, only subjects with available data will be included in the denominators).

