### **8.7.2 Clinical Laboratory Evaluations**

Central laboratory data will be utilized for all analyses. For the purposes of summarizing post-baseline maximum alkaline phosphatase (ALP), alanine aminotransferase (ALT), aspartate aminotransferase (AST), and total bilirubin and for the purposes of identifying cases of potential Hy's law, both central and local laboratory data will be used. In addition, local laboratory data

will be utilized in the assessment of any Potentially Clinically Significant (PCS) labs as defined in [Appendix B](#). Local laboratory data are collected on the eCRF: 1) if the subject did not meet the laboratory inclusion/exclusion criteria based on the central laboratory results, 2) potential Hy's law is reported based on local laboratory results, and 3) the Principal Investigator chooses to report local laboratory results obtained in the clinical management of the patient.

Laboratory values will be defined as potentially clinically significant (PCS) according to the table in [Appendix B](#). To be considered PCS, the laboratory value must meet both the lower limit and the percent decrease from baseline or both the upper limit and the percent increase from baseline. The proportion of subjects in the Safety Analysis Set with at least 1 PCS laboratory value will be summarized by treatment group and PCS laboratory values will be summarized by treatment group, laboratory parameter, visit and for the overall worst post-baseline value (minimum and maximum value, where appropriate defined in [Appendix C](#)). Percentages for each laboratory test will be based on the number of subjects with a baseline and post-baseline evaluation at the visit for the specific laboratory test. By-subject listings of all laboratory values for a subject with any PCS post-baseline laboratory value will also be provided.

Shift tables will be presented to show the number and percentage of subjects with a laboratory value below the lower limit of normal (LLN), within normal limits, above the upper limit of normal (ULN) and missing at baseline versus the value at each visit and the worst post-baseline value. Percentages for each laboratory test will be based on the number of subjects in the Safety Analysis Set.

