A listing of subjects who have the laboratory criteria for potentially meeting Hy's Law will also be provided. The laboratory criteria for potentially meeting Hy's Law is defined as ALT or AST  $>3 \times \text{ULN}$ , ALP  $\leq 2.0 \times \text{ULN}$  and total bilirubin  $>2 \times \text{ULN}$ . The proportion of subjects with any post-baseline AST  $>3 \times \text{ULN}$ ,  $>5 \times \text{ULN}$  and  $>10 \times \text{ULN}$ , any post-baseline ALT  $>3 \times \text{ULN}$ ,  $>5 \times \text{ULN}$  and  $>10 \times \text{ULN}$ , any post-baseline total bilirubin  $>1.5 \times \text{ULN}$  and  $>2 \times \text{ULN}$ , any post-baseline ALP  $>2 \times \text{ULN}$ , and any post-baseline ALT or AST value  $>3 \times \text{ULN}$  and any post-baseline total bilirubin value  $>2 \times \text{ULN}$  with an ALP  $\leq 2 \times \text{ULN}$  and with an ALP  $>2 \times \text{ULN}$  will be presented by treatment group.

Descriptive statistics for chemistry and hematology parameter values and the change from baseline at Day 4, EOT, and TOC will be summarized by treatment group for the Safety Analysis Set. Change from baseline will be calculated for each subject at the specified visit as the value at the specified visit minus the baseline value. The change from baseline to the minimum and maximum post-baseline values for chemistry and hematology parameters will also be summarized by treatment group. Change from baseline will be calculated for each subject as the minimum or maximum post-baseline value minus the baseline value. Baseline is defined as the last assessment prior to the first dose of study drug. Box-plots, which provide the median, mean, inter-quartile range, 5th and 95th percentile, and outliers will also be provided for ALP, AST, ALT, BUN, calcium, creatinine, phosphate, sodium, total bilirubin, absolute neutrophil count, hemoglobin, platelets, and WBC by scheduled study visit and treatment group.

Urinalysis data will be provided in a listing.

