- p: Blood samples sent to the local laboratory for the purposes of determining study eligibility must be repeated and sent to the central laboratory following enrollment. Collect blood and/or urine at LFU only if subject had an abnormal (high/low flag) result at TOC.
- q: **INPATIENTS:** On Day 4, blood and urine samples will be collected for safety laboratory evaluations.  
**OUTPATIENTS:** Blood and urine samples will be collected for safety laboratory evaluations at the study site visit scheduled 96 ± 24 hours after the first dose. *See Footnote c.*
- r: A urine pregnancy test will be performed at the site on all females unless surgically sterile or at least 2 years post-menopausal. A negative urine pregnancy test is required prior to randomization. Serum must be collected on Day 1 prior to 1st dose and sent to the central lab for confirmatory testing.
- s: Blood to be collected and sent to central laboratory for serologic tests for *M. pneumoniae*, *C. pneumoniae* and *L. pneumophila*.
- t: Collect blood samples (2 sets via peripheral venipuncture) for microbiologic culture and susceptibility testing at the local/regional lab at Baseline and as clinically indicated during the study. Repeat blood cultures after a positive result until sterilization is documented. If possible, subjects who are discontinued from study drug due to confirmed MRSA or MSSA bacteremia should have blood samples collected for microbiologic culture prior to switching to alternate appropriate therapy. All organisms isolated from blood cultures which are not considered contaminants will be sent to the central laboratory for confirmatory identification and susceptibility testing.

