**Safety Laboratory:**

Analysis Visit	Study Visit	Target Day	If scheduled study visit assessment not available:		
			Consider Unscheduled central assessment for Analysis Visit? 	Consider Local lab assessments for Analysis Visit?	Study Days acceptable for Analysis Visit
Baseline	Screening 	-	Yes	No	-4 to ≤1 
Day 4	Day 4 	4	Yes	No 	3 to 6
EOT 	EOT	-	Yes	No 	within 2 days after the last dose of study drug (i.e., last day of study drug through 2 subsequent calendar days)
TOC	TOC	-	Yes	No 	5-10 days after last dose of study drug
LFU	LFU	30	Yes	No 	27 to 33
Unscheduled 	-	-	Yes	Yes 	-

Notes: EOT: End of Treatment; TOC: Test of Cure; LFU: Late Follow-up; N/A: Not applicable.

 Except for Baseline, if more than 1 central measurement is taken during the visit window (and no scheduled is taken) the earliest value will be analyzed.

 Provided the date and time of collection is on or before the date and time of first dose

 The visit identified as the 96 +/- 24 hour visit (i.e., study visit Day 4, Day 5, or Day 6).

 Local labs assessment are to be included in the identification of worst post-baseline values (i.e. minimum, maximum, highest, lowest, any post-baseline, and PCS). See section 8.7.2.

 If an EOT assessment is done within the day 4 visit window, and no assessment was done at the study day 4 visit, the assessment will be reported at both the Day 4 and EOT analysis visits.

 Any unscheduled assessments not meeting the criteria for an analysis visit.

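### The by-visit table of potentially clinically significant laboratory values would give a Late Follow-Up percentage by arm in a subset selected mainly on an abnormal Test of Cure result, so it would not compare the randomized groups

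*SAP*

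**What the plan says.** **Who is sampled at LFU.** Protocol 6.13 states: "Blood and/or urine will be collected at LFU only if the subject had an abnormal (high/low flag) result at TOC". SAP Appendix A, footnote p, repeats the rule: "Collect blood and/or urine at LFU only if subject had an abnormal (high/low flag) result at TOC". Footnote p to Protocol Table 1 agrees. The laboratory row of the schedule has no routine mark at LFU.

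**What is tabulated.** SAP 8.7.2 says that "PCS laboratory values will be summarized by treatment group, laboratory parameter, visit and for the overall worst post-baseline value". The percentages use as denominator those with a baseline value and a value at the visit in question: "Percentages for each laboratory test will be based on the number of subjects with a baseline and post-baseline evaluation at the visit". This fits the general rule in SAP 7.6, where "only subjects with available data will be included in the denominators".

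**Which visits count.** The PCS text says only that the summary is by visit and does not list the visits. The safety laboratory table in SAP Appendix D has an LFU row with target Day 30 and acceptable Days 27 to 33, and an unscheduled central sample may fill it. SAP 7.2.3 also names LFU among the analysis visits. Nothing removes LFU from the by-visit PCS table or requires it to be labelled as a selected subset.

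**Contrasts within SAP 8.7.2.** The summary of values and changes stops at TOC: "Descriptive statistics for chemistry and hematology parameter values and the change from baseline at Day 4, EOT, and TOC". The shift tables use the whole Safety Analysis Set as denominator, and so does the proportion of subjects with at least one PCS value.

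**The concern.** At Day 4, EOT and TOC every subject is due a sample, so dividing by the subjects with a value is an ordinary observed-data percentage. At LFU most samples exist because the TOC result was abnormal. That result is measured after randomization and may itself depend on treatment. The same denominator rule then gives a percentage among subjects picked for having an abnormality, and the two arms may be picked at different rates.

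A table of late PCS values by arm, about three weeks after a 7-day course (Day 30 against Day 7), will be read as a comparison of late laboratory toxicity. It could show a difference that comes only from unequal flagging at TOC, or hide a real one. The other visits in the same table do not carry this risk, so a reader would have no warning.

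**Working it through.** **No figure to reproduce.** The documents state no PCS rate, no TOC flag rate and no precision for laboratory data. What follows shows direction and sensitivity; it does not estimate the bias.

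**Inputs.**
- N = 369 per arm: planned randomization (SAP 7.1), used for scale. SAP 7.1 expects under 1% to be excluded from the mITT Analysis Set, so the number treated should be close.
- q = share of subjects sampled at LFU: not in the documents; assumed 0.1 to 0.9.
- x = PCS cases among those sampled: not in the documents; assumed 6.
- f = PCS rate in unsampled subjects divided by the rate in sampled subjects: not in the documents; assumed 0, 0.25, 0.5 or 1.

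**Formulas.** With n the whole number of subjects nearest to qN:
- printed LFU rate = x / n
- all-subject rate = [x + (N − n) · f · x/n] / N
- ratio of printed to all-subject rate ≈ 1 / [q + (1 − q) f]

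**Step 1: level in one arm, x = 6.**

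| q | n sampled | printed rate | all-subject rate if f = 0 | ratio if f = 0 |
|---|---|---|---|---|
| 0.1 | 37 | 16.2% | 1.6% | 10.0 |
| 0.3 | 111 | 5.4% | 1.6% | 3.3 |
| 0.5 | 184 | 3.3% | 1.6% | 2.0 |
| 0.7 | 258 | 2.3% | 1.6% | 1.4 |
| 0.9 | 332 | 1.8% | 1.6% | 1.1 |

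At q = 0.5 the ratio falls to 1/(0.5 + 0.5 × 0.25) = 1.6 for f = 0.25 and to 1/(0.5 + 0.5 × 0.5) = 1.3 for f = 0.5. At f = 1 it is 1.0, meaning no overstatement at all.

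**Step 2: between arms, f = 0.**
- Equal true counts, 6/369 = 1.6% in each arm, flag shares 30% and 50%: 6/111 = 5.4% against 6/184 = 3.3%, an artificial gap of 2.1 points. Swapping the flag shares reverses its sign.
- Equal true counts, flag shares 50% and 60%: 6/184 = 3.3% against 6/221 = 2.7%, a gap of about 0.5 points.
- Equal true counts and equal flag shares of 40%: 6/148 = 4.1% in both arms, no gap.
- Unequal true counts, 9/369 = 2.4% against 6/369 = 1.6%, flag shares 60% and 40%: 9/221 = 4.07% against 6/148 = 4.05%. The real difference disappears.

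**Step 3: how large q might be.** The sampling rule refers to an abnormal TOC result without naming a test, and the documents do not say whether the full panel or only the abnormal test is repeated. If one flag triggers the full panel, q could be large. SAP Appendix C lists 32 hematology and chemistry parameters; assuming independent tests each flagged 5% of the time, q = 1 − 0.95^32 = 0.81, and the ratio is at most about 1/0.81 ≈ 1.2. If only the flagged test is repeated, the denominator for each parameter is much smaller and the ratio correspondingly larger.

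**The case against.** **The LFU row is inferred.** The PCS text says only that values are summarized by visit, and where SAP 8.7.2 names laboratory visits it stops at TOC. The LFU row in Appendix D also serves the worst post-baseline summaries. This is fair as far as it goes: the fault is an open visit list, not an express instruction to print an LFU percentage. But Appendix D does define LFU as an analysis visit and nothing excludes it, so a programmer following the text would produce the row.

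**Inflation is not established.** A reader might infer that the LFU rates are inflated in both arms by a known factor. The documents do not support that. Overstatement requires unsampled subjects to have a lower PCS rate. That is plausible, because the PCS limits in Appendix B lie outside the normal range, but it is not certain: PCS also requires a change from baseline (for low values, "To be considered PCS, the laboratory value must meet both the lower limit and the percent decrease from baseline"). The factor depends on flag rates that are not given.

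**Sampling is not confined to flagged subjects.** Unscheduled central samples in Days 27 to 33 can count as LFU, and Protocol 6.13 allows extra tests at the investigator's discretion. This stands, but such samples are not routine either.

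**The box plots.** A reader might infer that they share the defect. They are planned by scheduled study visit, and the schedule has no routine LFU laboratory mark, which points to leaving LFU out. SAP 7.2.3, on the other hand, gives LFU as an example of a scheduled visit. The wording is ambiguous, not wrong.

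**The harm is limited.** No inferential laboratory comparison is planned, and other summaries use the full Safety Analysis Set. This is correct and keeps the point small.

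**Conclusion.** The point holds in a limited form. Followed as written, the SAP yields an LFU PCS percentage by arm in a subset selected mainly on a flagged TOC result. That percentage is not a comparison of the randomized groups, whatever the flag rate. It would probably exceed the rate expected had everyone been sampled, on the assumption that unsampled subjects have fewer PCS values. Under the assumed inputs the excess runs from about 1.1-fold to 10-fold if unsampled subjects have none, and vanishes if their rate is the same. No single figure can be taken from the documents.

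The scope is one descriptive safety table. The Day 4, EOT and TOC PCS rates and the shift-table denominators do not have this problem. The efficacy analyses are untouched, and the documents do not support reading this as a defect of the laboratory safety analysis as a whole. It is a minor point, worth correcting because the correction is so cheap.

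**What to change.** - State in SAP 8.7.2 that by-visit PCS percentages are produced for Day 4, EOT and TOC only, matching the visits already named there for descriptive statistics. For clarity, say the same of the box plots.
- Present LFU laboratory results as a listing, or as a follow-up summary of subjects with an abnormal TOC result. Show the number sampled per arm and state that it is not a between-arm comparison.
- Keep LFU values in the worst post-baseline summary, with a note that LFU sampling was conditional, since flagged subjects have one more chance of a PCS value.
- Do not use all subjects with a TOC value as the LFU denominator. That would count every unsampled subject as free of PCS values and replace a possible overstatement with a possible understatement.

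The cost is a sentence or two in the SAP and a change to the table shells. No new data and no change in trial conduct are needed.

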### 8.7.3 ECG Parameters

ECG data are being read centrally. The mean of the triplicates (or if triplicates not available, the duplicates or single ECG, whichever is available) will be used for all analyses, even if not performed within a 5-minute interval. Descriptive statistics for heart rate, PR interval, QRS interval, QT interval, and QT interval corrected by the Fridericia formula (QTcF) and the change from baseline at Day 1 (1-3 hours after the first dose of study drug), Day 4 (inpatients)/96±24h after the first dose of study drug (outpatients) (prior to the first dose of study drug) and Day 4 (1-3 hours after the first dose of study drug) will be summarized by treatment group for subjects in the Safety Analysis Set. In addition, Day 4 post-active dose will be summarized. Change from baseline will be calculated for each subject at Day 1 (1-3 hours after the first dose of study drug) and Day 4 (inpatients)/96±24h after the first dose of study drug (outpatients) (prior to and 1-3 hours after the first dose of study drug) as the value at the specified visit and time point minus the baseline value. The change from baseline to the minimum and maximum post-baseline values will also be summarized by treatment group, where these post-baseline values include unscheduled visits. Change from baseline will be calculated for each subject as the minimum or maximum post-baseline value minus the baseline value. Baseline is defined as the mean of the triplicates from the last assessment prior to the first dose of study drug. ECG parameters for each of the triplicates (including the change in QTcF value from pre-dose to post-dose) and the overall interpretation of the ECG will be presented on a listing.

The number and percentage of subjects with any post-baseline increase in QTcF and any post-baseline increase of >30 msec or >60 msec in QTcF will be summarized by treatment group. The number and percentage of subjects with a post-baseline QTcF of >480 msec or >500 msec will also be summarized by treatment group. The number and percentage of subjects with a post-baseline increase in QTcF of >30 msec resulting in a post-baseline QTcF of >480 msec or >500 msec as well as QTcF of >60 msec resulting in a post-baseline QTcF of >480 msec or >500 msec will also be summarized by treatment group. The distribution of QTcF values ( $\leq 450$  msec,  $>450 - \leq 480$  msec,  $>480 - \leq 500$  msec, and  $>500$  msec) at each time point and the distribution of change from baseline in QTcF values at each time point (0 or less (no increase),  $1 - < 30$  msec,  $30 - 60$  msec, and  $>60$  msec) will be summarized by treatment group for subjects in the Safety Analysis Set. These analyses will also be provided by study visit.

A listing will be provided of findings identified on the ECG.

### 8.7.4 Vital Signs

Descriptive statistics for temperature, respiratory rate, heart rate, diastolic blood pressure, systolic blood pressure, and the change from baseline at each post-baseline visit will be summarized by treatment group for all subjects in the Safety Analysis Set. Change from baseline will be calculated for each subject at the specified visit as the value at the specified visit minus the baseline value. The change from baseline to the minimum and maximum post-baseline values will also be summarized by treatment group. Change from baseline will be calculated for each subject as the minimum or maximum post-baseline value minus the baseline value. Baseline is defined as the last assessment prior to Day 1.

Post-baseline vital signs will be defined as high or low if the criterion value listed in Table 11 is met. All vital signs will be presented in a listing with a flag for high and low indicating the criterion value was met. PCS is defined as meeting both the criterion value and the change from baseline criterion listed in Table 11. The number and percentage of subjects with any post-baseline PCS vital sign will be presented by treatment group. The overall post-baseline incidence of PCS values, which includes values from unscheduled post-baseline visits, will be summarized by treatment group for the Safety Analysis Set, and all PCS vital sign values will be listed and flagged in by subject listings.

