## 7.2 Visit Windows

### 7.2.1 Baseline

Unless otherwise stated below, baseline is defined as the last measurement prior to the first dose of study drug.

- For microbiological pathogen determination, baseline is defined as the 24-hour period prior to the administration of the first dose of study drug and the 24 hours after the first dose of study drug. A pathogen identified from a respiratory (pleural fluid, bronchoalveolar lavage (BAL), sputum), blood for culture, urine, nasopharyngeal or oropharyngeal specimen collected at baseline is considered a baseline pathogen. An atypical pathogen identified by serology is considered a baseline pathogen if the baseline

sample is collected in the 24-hour period prior to or the 24 hours after the administration of the first dose of study drug.

- For vital signs, baseline is defined as the Screening assessment (since time of assessment is not captured) as long as the date of collection is on or before the date of first dose of study drug.
- For ECGs, baseline is defined as the mean of the triplicates (or duplicate or single, if a triplicate is not obtained) from the last assessment prior to the first dose of study drug, including scheduled and unscheduled visits.
- If no study drug is received, baseline is defined as the measurement taken at the Screening Visit (ie, prior to the randomization date/time)

Study Day 1 is defined as the first calendar day of study drug administration (or the date of randomization if no study drug was received). The calendar day prior to the first dose of study drug (or randomization day if no study drug is received) is Study Day -1; there is no Study Day 0.

For all clinical assessments and procedures performed prior to the date of the first study drug administration, study day will be calculated as the date of the assessment minus the date of the first dose of study drug. For all clinical assessments and procedures performed on or after the date of the first dose of study drug, study day will be calculated as the date of the assessment minus the date of the first dose of study drug, plus 1.

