## **8.7 Safety Analyses**

All safety analyses will be conducted in the Safety Analysis Set. Subjects who receive the wrong study drug for their entire course of treatment will be analyzed in the group based on the drug received. Subjects who receive the wrong study drug less than the entire course of treatment will be analyzed in the as randomized treatment group.

For each safety parameter with the exception of ECGs which are measured in triplicate at each time point and vital signs which uses the last assessment prior to Day 1, the last assessment made prior to the first dose of study drug will be used as the baseline for all analyses.

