- d: Perform End of Treatment (EOT) assessments at the study site within 1 day (up to 2 days permitted) after the last dose of study drug or at the time of premature discontinuation of study drug or early withdrawal from study. EOT assessments resulting from premature discontinuation of study drug should be done in place of the regular study visit on Days 1 to 7.
- e: Perform Test of Cure (TOC) assessments at the study site 5–10 days after the last dose of study drug. All subjects will have a TOC Visit irrespective of early clinical failure or receipt of an alternative antibiotic.
- f: Perform Late Follow Up (LFU) assessments at the study site on Day 30 ± 3 days. All subjects will have a LFU Visit irrespective of early clinical failure or receipt of an alternative antibiotic.
- g: Obtain informed consent before initiating any study-specific assessments or procedures.
- h: Assessment or procedure may occur at either Screening OR prior to the first dose of study drug on Day 1 once eligibility has been determined.
- i: All subjects will have vital signs and O2 saturation evaluated at Screening/Baseline and Day 1. If screening/baseline and Day 1 occur on the same calendar day, vital signs and O2 saturation do not need to be repeated. All subjects will also have assessments at EOT and TOC; at LFU, vital signs should be performed if medically indicated. If EOT and the last day of study drug are the same day, vital signs do not need to be repeated, they may be recorded once on that day (i.e., as part of the EOT assessment). Record the vital signs associated with the highest temperature after the first dose of study drug.  
**INPATIENTS:** Vital signs, O2 saturation, and supplemental O2 usage will be measured daily. If multiple vital signs are taken on a study day, the highest temperature and the vital signs associated with that high temperature will be recorded.  
**OUTPATIENTS:** In addition to the above time points, vital signs, O2 saturation and, if applicable, supplemental O2 usage will be measured at the study visit scheduled 96 ± 24 hours after the first dose of study drug.

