## APPENDIX D: SAFETY ASSESSMENT WINDOWS

### Vital Signs:

Analysis Visit	Study Visit	Target Day	If scheduled study visit assessment not available:	
			Consider Unscheduled assessment for Analysis Visit?	Study Days acceptable for Analysis Visit 
Baseline	Screening 	-	No	-
Day 1	Day 1	1	Yes	1
Day 2	Day 2	2	Yes	2
Day 3	Day 3	3	Yes	3
Day 4	Day 4	4	Yes	4
Day 5	Day 5	5	Yes	5
Day 6	Day 6	6	Yes	6
Day 7	Day 7	7	Yes	7
EOT	EOT	-	Yes	within 2 days after the last dose of study drug (i.e., last day of study drug through 2 subsequent calendar days)
TOC	TOC	-	Yes	5-10 days after last dose of study drug
Unscheduled 	-	-	Yes	

Notes: EOT: End of Treatment; TOC: Test of Cure; N/A: Not applicable.

 Except for Baseline, if more than 1 measurement is taken during the visit window (and no scheduled is taken) the earliest value will be analyzed..

 Provided the date of collection is on or before the date of first dose

 Any unscheduled assessments not meeting the criteria for an analysis visit.

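### SAP 8.7 and 8.7.4 take vital-sign baseline from before Day 1, whereas 7.2.1 and Appendix D also accept a Screening value from the dosing day; read literally, 8.7.4 leaves subjects screened that day with no baseline

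*SAP*

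**What the plan says.** The SAP defines vital-sign baseline in four places.

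- **8.7.4 Vital Signs:** "Baseline is defined as the last assessment prior to Day 1".
- **8.7 Safety Analyses:** the general safety baseline is the last assessment before first dose. Vital signs are named as an exception: "vital signs which uses the last assessment prior to Day 1".
- **7.2.1 Baseline:** "For vital signs, baseline is defined as the Screening assessment (since time of assessment is not captured"; the date condition follows: "as long as the date of collection is on or before the date of first dose of study drug".
- **Appendix D, vital signs table:** Baseline maps to the Screening visit, unscheduled assessments are not considered for it, and the footnote reads "Provided the date of collection is on or before the date of first dose".

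Two further provisions decide whether these differ in practice. SAP 7.2.1 fixes the calendar meaning of the day: "Study Day 1 is defined as the first calendar day of study drug administration". Appendix A, footnote i, covers screening on the dosing day with a clause that opens "If screening/baseline and Day 1 occur on the same calendar day, vital signs" and goes on to waive the repeat measurement. Protocol 6.5 has the same waiver.

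**The concern.** Sections 8.7 and 8.7.4 agree with each other, so this is not a single slip, and they are where a programmer building the vital-sign tables would look. Protocol Section 3 allows screening within the 24 hours before first dose, and Protocol 5.4 asks for dosing as soon as possible after diagnosis, so screening on the dosing day is an expected case. Such a subject may have only one pre-dose set of vital signs, dated Day 1. Under 7.2.1 that set is the baseline; under 8.7.4 it is not before Day 1 and does not qualify.

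Two outputs depend on it. Change from baseline cannot be computed without a baseline. PCS status in 8.7.4 requires both the criterion value and the change from baseline in Table 11, so a subject without a baseline can never be a PCS case. Two programmers working from different sections of one SAP would produce different safety tables.

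**Working it through.** The plan gives no figure to reproduce, so the check compares the two rules case by case and then scales the consequence.

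**Step 1. The two rules**

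| Subject | 7.2.1 and Appendix D | 8.7 and 8.7.4, read literally |
|---|---|---|
| Screened on the calendar day before dosing, no other pre-dose value | Screening value | Screening value (same) |
| Screened the day before, with a later unscheduled value still before Day 1 | Screening value (unscheduled not considered) | The unscheduled value, as the last one |
| Screened on the dosing day, vital signs not repeated | Screening value | None |

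The rules give different results in the second and third rows. The third matters more, because it removes the baseline.

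**Step 2. Is the gap filled elsewhere?** No. SAP 7.6 leaves missing values for these outcomes unimputed and uses observed values only. The other safety baselines do not have this gap: laboratory and ECG baselines in 8.7.2 and 8.7.3 are tied to the first dose, and Appendix D accepts pre-dose values on Day 1 for both.

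**Step 3. Number of subjects.** Let s be the share screened on the dosing day without repeat vital signs. The documents do not give s. Using the planned 738 randomized subjects as the scale (the Safety Analysis Set will be slightly smaller, since it needs at least some study drug):

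- s = 10%: 0.10 × 738 = 73.8, about 74 without a baseline
- s = 50%: 0.50 × 738 = 369
- s = 90%: 0.90 × 738 = 664.2, about 664

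Under 7.2.1 the number lost from this cause is 0 at any s.

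**Step 4. PCS percentage.** Let N be the size of the Safety Analysis Set and p the true PCS proportion, assumed for illustration to be the same whichever day screening took place.

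- PCS cases that can be counted under 8.7.4: (1 − s) × N × p
- Full Safety Analysis Set as denominator: (1 − s)Np / N = (1 − s)p. For s = 10%, 50% and 90% this is 0.90p, 0.50p and 0.10p.
- Reduced denominator (subjects with available data, SAP 7.6): (1 − s)Np / ((1 − s)N) = p. The percentage is not lowered, but it rests on fewer subjects and describes only those screened on an earlier day.

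Section 8.7.4 does not state a denominator for subjects with no baseline. By contrast, 8.7.2 restricts laboratory PCS percentages to subjects with both a baseline and a post-baseline value.

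**The case against.** The strongest reply is that the matter is already settled. Section 7.2.1 is the dedicated baseline section, gives a reason for its vital-sign rule, and is repeated in Appendix D, to which 7.2.2 sends the reader for safety windows. On that view every subject screened on the dosing day has a baseline and 8.7.4 is only a loose paraphrase.

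A reading that reconciles the sections is also available. Section 7.2.2 says analyses use the nominal visit, 7.2.3 lists Baseline and Day 1 as separate analysis visits, and Appendix D maps Baseline to Screening. If Day 1 in 8.7.4 means the Day 1 visit, the assessment before it is Screening, as in 7.2.1. That would also explain why vital signs are singled out in 8.7: with no clock time recorded, a Day 1 value cannot be shown to be pre-dose.

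Part of this stands. The loss of baseline occurs only if 8.7 and 8.7.4 are programmed in preference to 7.2.1 and Appendix D. But no section states an order of precedence or the nominal-visit meaning. The SAP's definition of Study Day 1 is a calendar day, and Appendix A, footnote b, also calls Day 1 the first day of drug administration. Even on the nominal-visit reading, taking the last assessment could select an unscheduled value that Appendix D excludes.

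A reader might also infer that more than half of the Safety Analysis Set would lose the analysis. With first doses uniform over 08:00–20:00 (mean 14 h after midnight) and a screening-to-dose gap uniform over 0–24 h, the same-day share is 14/24 = 58%; gaps limited to 12 h or 6 h give 94% or 100%. The documents support neither distribution. Spreading doses evenly over the day instead gives 12/24 = 50%, so such figures reflect the assumptions chosen.

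**Conclusion.** The conflict is real, and the rule in 8.7 and 8.7.4 gives a wrong result when followed literally: subjects screened on the dosing day have no vital-sign baseline, no change from baseline and no possible PCS classification. The number depends on an unknown share; 74 to 664 of 738 corresponds to an assumed 10% to 90%. It is zero if 7.2.1 and Appendix D are what is programmed.

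Three stronger inferences are not supported:

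- **That PCS incidence would necessarily be understated.** The count falls, but the percentage is lowered only with the full Safety Analysis Set as denominator. The reduced-denominator rule in SAP 7.6 would instead change whom the percentage describes. High and low flags on the criterion value alone, and the listing of all vital signs, need no baseline and remain available.
- **That the treatment comparison would be biased.** The timing of screening precedes treatment, so the loss does not depend on assigned arm in this randomized, double-blind study.
- **That efficacy is affected.** The primary ECR analysis, the non-inferiority test and power do not use this baseline. ECR plus improvement in vital signs (SAP 6.3.2) does use baseline vital signs, but 8.7 and 8.7.4 are safety sections, so the general definition in 7.2.1 would normally apply there.

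The point is therefore confined to descriptive vital-sign safety summaries. It should be corrected before programming.

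**What to change.** Replace the baseline sentence in SAP 8.7.4 and the vital-sign clause in SAP 8.7 with the rule already in 7.2.1 and Appendix D: the Screening assessment, provided it is dated on or before the date of first dose. A cross-reference to 7.2.1 and Appendix D would do equally well. One definition then applies throughout.

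The cost is two wording edits. No new data, visit or analysis is needed, and SAP 1.0 already provides for documenting changes in an amendment before database lock.
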